10.2.4 Dose Modifications for Hematologic Toxicity

The study chair must be notified for any dosage modification or use of myeloid growth factors.

- If a subject experiences a dose modifying hematologic toxicity as defined in [Section 10.2.2](#), the treatment will be held until improvement to Grade 3 or less.
- Subjects will be allowed 1 episode of Grade 4 hematologic toxicity without dose reduction.
- If there is > 1 hold for Grade 4 hematologic toxicity, dose will be reduced per guidance in [Appendix II](#). Counts should be checked twice weekly during this time.
- Doses reduced for toxicity will not be re-escalated, even if there is minimal or no toxicity with the reduced dose.
- If dose-modifying toxicity recurs in a subject who has resumed treatment at the reduced dose, the subject must be removed from protocol therapy.

10.2.5 Dose Modifications for Hepatic Toxicity

If a subject experiences Grade ≥ 3 ALT or AST or total bilirubin elevation, treatment will be held. If toxicity resolves to meet eligibility criteria within 7 days, the drug may be resumed at the same dose. Grade ≥ 3 ALT or AST or bilirubin that persists ≥ 7 days will be considered dose-modifying and require dose modification per [Section 10.1.3](#).

Grade	0	1	2	3	4
SGOT (Serum glutamic oxaloacetic transaminase) (AST)	WNL	>ULN to 3x ULN	>3 to 5x ULN	>5 to 20x ULN	>20x ULN
SGPT (Serum glutamic pyruvic transaminase) (ALT)	WNL	>ULN to 3x ULN	>3 to 5x ULN	>5 to 20x ULN	>20x ULN
Bilirubin	WNL	>ULN to 1.5x ULN	>1.5 to 3x ULN	>3 to 10x ULN	>10x ULN

Safety Follow-Up Procedures for subjects with ALT or AST ≥ 3 times ULN or bilirubin ≥ 1.5 times ULN:

- Monitor subjects weekly until liver chemistries resolve, stabilize, or return to within baseline values.

Safety Follow-Up Procedures for subjects meeting DLT criterion as above (ALT or AST ≥ 5 times ULN and bilirubin ≥ 3 times ULN) greater than 7 days:

- This event is considered an DLT.
- Serum bilirubin fractionation should be performed if testing is available. If fractionation is unavailable, urinary bilirubin is to be measured via dipstick (a measurement of direct bilirubin, which would suggest liver injury).
- Subjects should have close follow-up for repeat liver chemistries, additional testing, and close monitoring (with specialist or hepatology consultation recommended).
- Monitor subjects twice weekly until liver chemistries (ALT, AST, ALP, and bilirubin) resolve, stabilize or return to within baseline values.

- In addition, every attempt should be made to carry out the liver event follow-up assessments described below:
 - Viral hepatitis serology, including:
 - Hepatitis A IgM antibody
 - Hepatitis B surface antigen and Hepatitis B Core Antibody (IgM)
 - Hepatitis C RNA
 - Cytomegalovirus IgM antibody
 - Epstein-Barr viral capsid antigen IgM antibody (or if unavailable, then obtain heterophile antibody or monospot testing)
 - Serum creatine kinase (CK) and lactate dehydrogenase (LDH).
 - Fractionate bilirubin, if total bilirubin ≥ 2 X upper limit of normal (ULN).
 - Obtain a complete blood count (CBC) with differential to assess eosinophilia.
 - Record the appearance or worsening of clinical symptoms indicative of hepatitis or hypersensitivity, such as fatigue, nausea, vomiting, right upper quadrant pain or tenderness, fever, rash or eosinophilia as relevant on the AE CRF.
 - Record the use of concomitant medications, including acetaminophen, herbal remedies or any other over the counter (OTC) medications, or any putative hepatotoxins, on the concomitant medication CRF.
 - In the appropriate clinical setting optional assessments as below should be considered:
 - Anti-nuclear antibody, anti-smooth muscle antibody, and Type 1 anti-liver kidney microsomal antibodies.
 - Liver imaging (ultrasound, MRI or CT) to evaluate liver disease.
 - Serum acetaminophen adduct High Performance Liquid Chromatography (HPLC) assay (quantifies potential acetaminophen contribution to liver injury in subjects with definite or likely acetaminophen use in the preceding week).

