10.2 Dose Reduction

10.2.1 Definition of Dose-Modification Toxicity

Dose-modification toxicity will be defined as any of the following events that are possibly, probably or definitely attributable to trametinib.

Dose modifying hematological and non-hematological toxicities are defined differently.

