10.2.1.1 Non-Hematological Dose-Modifying Toxicity

- See [Section 10.2.6](#) for management guidelines for toxicities of special interest. Note that dose modification or discontinuation of trametinib for toxicity is considered a dose modifying toxicity.
- Any Grade 4 non-hematological toxicity with specific exclusion of:
 - Grade 4 fever/pyrexia that resolves to Grade < 2 within 72 hours with supportive care (anti-pyretics)
- Dose-modifying hypertension will be considered as the following:
 - Grade 4 hypertension,
 - A blood pressure > 25 mm Hg above the 95th percentile for age, height, and gender, confirmed by repeated measurement

Note: if elevated, take 3 serial blood pressure readings from the same extremity with the patient in the same position, separated by at least 5 minutes. Avoid using the lower extremity if possible. Use the mean average of the 3 measurements.

- Any Grade 3 non-hematological toxicity with the specific exception of:
 - Grade 3 nausea and vomiting of less < 3 days duration

- Grade 3 fever or infection < 7 days duration.
- Grade 3 hypophosphatemia, hypokalemia, hypocalcemia and/or hypomagnesemia responsive to oral supplementation within 7 days
- Grade 2 allergic reactions that necessitate discontinuation of study drug will not be considered a dose-modifying toxicity
- Any Grade 2 non-hematological toxicity that persists for ≥ 7 days and is considered sufficiently medically significant or sufficiently intolerable by patients that it requires treatment interruption
- Grade 2 left ventricular ejection fraction disease
- Grade 2 cardiac valvular toxicity (mitral/aortic/tricuspid)
- Grade 2 pneumonitis
- Treatment interruption longer than 14 days due to delayed recovery from toxicity will be cause for dose modification

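### Section 10.2.5 restates its persistent liver-toxicity criterion with AND where it had OR, which leaves isolated Grade 3 or 4 elevations in the weekly follow-up tier; its same-dose restart is also not reconciled with the general dose rules

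*Protocol*

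**What the plan says.** Section 10.2.5 has three layers.

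- **Hold and restart.** Grade 3 or higher ALT, AST or total bilirubin means the drug is held. If values return to the eligibility limits within 7 days, "the drug may be resumed at the same dose".
- **Dose-modifying criterion.** Grade 3 or higher "ALT or AST or bilirubin that persists" for 7 days or more is dose-modifying. The modification is to follow section 10.1.3.
- **Follow-up tiers.** The lower tier starts at ALT or AST 3 times ULN, or bilirubin 1.5 times ULN: "Monitor subjects weekly until liver chemistries resolve, stabilize, or return to within baseline values". The upper tier is for subjects "meeting DLT criterion as above (ALT or AST ≥ 5 times ULN and bilirubin ≥ 3 times ULN) greater than 7 days". It adds "Monitor subjects twice weekly until liver chemistries (ALT, AST, ALP, and bilirubin) resolve" or stabilize, bilirubin fractionation, a recommended specialist or hepatology consultation, viral serology, CK and LDH, and further items.

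The general rules sit elsewhere. Section 10.2.1 defines dose-modification toxicity as "any of the following events that are possibly, probably or definitely attributable to trametinib". Section 10.2.1.1 then includes "Any Grade 4 non-hematological toxicity with specific exclusion of" one kind of transient fever, and "Any Grade 3 non-hematological toxicity with the specific exception of" a short list with no liver entry. Section 10.2.3 provides for restart at the next lower dose. Section 10.10 asks for recovery to Grade 0-1 and one level lower after Grade 3. After Grade 4 it asks for the same or for permanent discontinuation.

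**The concern.** The upper-tier heading says it repeats a criterion stated above it, but no criterion above it requires transaminase and bilirubin elevation together. A site applying the heading as printed would leave a subject with severe, persistent but isolated enzyme or bilirubin elevation in the lower tier. That subject would miss the work-up meant to find the cause of the liver injury.

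The restart rule raises a second, smaller question. For the same brief liver event, one section permits the dose to stay unchanged and others call for a reduction. The protocol lists 25 sites, so different readings are a practical possibility. Section 1.2.2 reports hepatic toxicity as the most frequent Grade 3/4 event (9%) in an adult trial in myeloid malignancies. That is another population and gives no rate for this one, but it shows that the event is foreseeable.

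**Working it through.** There is no stated figure to reproduce. The check applies the printed rules to cases.

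**Inputs (10.2.5 grade table).** ALT and AST: Grade 3 is above 5 to 20 times ULN, Grade 4 above 20. Bilirubin: Grade 3 is above 3 to 10 times ULN, Grade 4 above 10.

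**Rules.**
- Held: any one marker at Grade 3 or higher.
- Dose-modifying: held and lasting at least 7 days.
- Upper tier as printed: (ALT or AST at least 5) AND bilirubin at least 3, for more than 7 days.
- Upper tier with OR: the same thresholds joined by OR, for more than 7 days.

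**Cases at day 10 (multiples of ULN, other markers normal).**

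| Case | Held | Dose-modifying | Upper tier as printed | Upper tier with OR |
|---|---|---|---|---|
| ALT 10 | yes | yes | no | yes |
| AST 10 | yes | yes | no | yes |
| ALT 25, AST 25 | yes | yes | no | yes |
| Bilirubin 5 | yes | yes | no | yes |
| Bilirubin 12 | yes | yes | no | yes |
| ALT 10, bilirubin 2.5 | yes | yes | no | yes |
| ALT 10, bilirubin 5 | yes | yes | yes | yes |

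Only the last case reaches the upper tier as printed. The other six enter only the weekly tier. At exactly day 7 every case is dose-modifying, yet none is in the upper tier under either connective, because the heading asks for more than 7 days. The duration therefore needs correcting too.

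**Is AND intended?** Two features of 10.2.5 say not. The heading refers back rather than setting a new threshold. The work-up list also asks for bilirubin fractionation if total bilirubin is at least 2 times ULN, a condition that would always be met if entry already required 3 times ULN.

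**Cross-reference.** Section 10.1 contains only 10.1.1 and 10.1.2, so 10.1.3 does not exist. Section 10.2.3 covers the subject.

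**Restart.** Take an attributable ALT of 6 times ULN (Grade 3) that falls to 2.5 on day 4. It meets the ALT eligibility limit (at most 3) and is Grade 1, so every section's recovery level is reached. Section 10.2.5 permits the same dose; 10.2.3 and 10.10 call for one level lower. The labelled step is 1 - 0.020/0.025 = 20%. In the Appendix II rows from 10.0 kg up, it runs from 1 - 0.2/0.2 = 0% (10.0-10.9 kg) to 1 - 1/1.5 = 33% (50.1-70 kg). These figures describe how far the texts differ on dose; they do not measure harm.

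**Grade 4.** Section 10.2.5 sets no upper grade for same-dose restart. To go from just above the Grade 4 boundary to the eligibility limit within 7 days, the fall must be at least:
- AST: 1 - 5/20 = 75%
- ALT: 1 - 3/20 = 85%
- Bilirubin: 1 - 1.5/10 = 85% (Gilbert's syndrome aside)

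The route is open on paper but narrow.

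**The case against.** **On follow-up.** A reader might infer that an isolated elevation receives nothing beyond weekly checks. The protocol does not support that. The drug is held at once and the event is dose-modifying from day 7. Section 10.2.3 removes a subject who has not recovered within 14 days, and section 10.3 continues follow-up until resolution or stabilization. Grade 4 events go to the DSMB within 5 calendar days (11.4.1). CK, CBC with differential and total bilirubin are already in Table 6-1, and several upper-tier items are recommendations or best efforts. The weekly tier describes the follow-up schedule alone. A deliberately stricter upper tier is conceivable, but the back-reference in the heading speaks against it.

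**On restart.** The opposing case is strong and largely stands. Section 10.2.5 is the organ-specific rule and says when a liver event counts as dose-modifying. It only permits the same dose, so a site that reduces satisfies all the sections. Other organ-specific rules also depart from the general restart dose: Grade 3 diarrhea that resolves within 72 hours may restart without reduction.

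Two stronger inferences fail:
- The exception clauses in 10.2.3 that point to 10.2.6 might seem to show that 10.2.5 yields. They attach to removal at 14 days and to re-escalation, and do not touch the restart dose.
- A second brief event might seem to mean removal under 10.2.3. That clause needs a recurring dose-modifying toxicity, which a brief event is not under 10.2.5, so the inference presumes the disputed reading.

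What remains is that 10.2.1.1 has no liver exception, 10.10 has none either, and 10.2.5 is silent on Grade 4.

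**Conclusion.** The follow-up criterion in 10.2.5 is wrong as written. It changes OR to AND and at least 7 days to more than 7 days while claiming to restate the criterion. Taken literally, it keeps isolated persistent Grade 3 or 4 elevations out of twice-weekly chemistries, viral serology, LDH and the recommended hepatology consultation, and keeps isolated bilirubin elevations out of the fractionation step. This is a wording error in a safety rule, cushioned by the hold, the dose modification and the removal rule, and it should be corrected.

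The restart point is secondary. It is a real inconsistency for events at least possibly attributable to trametinib, best settled by confirming 10.2.5 as the governing rule. Grade 4 is the exception: 10.2.3 and 10.10 both require reduction or discontinuation there.

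The protocol gives no liver-event rate for this population, so affected subjects cannot be counted. A reader might infer from the DLT label in 10.2.5 that toxicity monitoring is also affected. It is not: the stopping rule in 9.2 uses its own event list. No endpoint, analysis or error rate changes.

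**What to change.** 1. In 10.2.5, replace the parenthesis and duration in the upper-tier heading with: Grade 3 or higher ALT or AST or bilirubin persisting 7 days or more.
2. Correct the reference to section 10.1.3 to section 10.2.3.
3. Add one sentence to 10.2.1.1 and to 10.10 stating that 10.2.5 governs hepatic events.
4. In 10.2.5, limit same-dose restart to Grade 3, leaving Grade 4 to reduction or discontinuation as in 10.2.3 and 10.10.

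The cost is a wording amendment and some extra liver tests in subjects with an isolated persistent elevation. Sample size, endpoints and analyses are untouched.

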10.2.6 Guidelines and Dose Modifications for Trametinib Events of Special Interest

Dose modification and adverse event (AE) guidelines are outlined in the sections below for AEs that are deemed events of special interest including:

- Rash
- Creatinine Kinase (CK) or Creatinine Phosphokinase (CPK) elevations
- Ejection Fraction Changes
- Pneumonitis
- Diarrhea
- Visual Disturbances
- Hypertension
- Paronychia

10.2.6.1 Treatment Dose Modifications and Guidelines for Rash

Dermatologic complications are the most frequent adverse events in subjects receiving trametinib and so both proactive/prophylactic ([Section 10.1.6.2](#)) and reactive ([Section 10.1.6.3](#)) approaches will be taken. Rashes associated with trametinib have included many different types and can begin as early as cycle 1 or 2. Descriptions include: erythematous rash, maculopapular rash, pruritic rash, acneiform dermatitis, exfoliative rash. Grade 3 rashes are often associated with pruritus and can have scaling. Based on the experience on the current adult Phase I/II study the following recommendations should be followed. For Grade 3 rash trametinib should be held until resolution to Grade 1 or better and then treatment can be resumed at a reduced dose as outlined in the dose reduction table ([Appendix II](#)). For eczematous rashes, moisturizers or low-dose topical corticosteroids may be used if based on the rash appearance they would be considered appropriate treatment. For pustular rash, topical clindamycin gel or lotion may be applied twice daily. For more severe cases, oral tetracyclines may be useful in older children. Ketoconazole shampoo may be used for scalp rash. If oral corticosteroids are required for severe rash, trametinib should be held until improvement to < Grade 1 at a reduced dose as outlined in the dose reduction table ([Appendix II](#)).

10.2.6.2 Prophylactic Treatment to Prevent Dermatologic Toxicity (Rash)

- 1) All subjects should avoid unnecessary sunlight and use sunscreen whenever there is possible exposure. Broad-spectrum sunscreen with skin protection factor (SPF) ≥ 30 should be applied at least twice daily if subject will be exposed to sun.
- 2) Recommend a thick, alcohol-free emollient cream (e.g., glycerine and cetomacrogol cream) on dry areas of the body at least twice daily. For prepubescent subjects may consider bleach baths.
 - a. Add $\frac{1}{4}$ to $\frac{1}{2}$ cup of regular strength bleach to a full bathtub (or approximately 1 teaspoon per gallon) and soak for 5-10 minutes
 - b. Recommended frequency is three times per week
 - c. Follow immediately by alcohol-free hypoallergenic skin moisturizer as above
- 3) Non-alcohol containing mouth rinse (e.g. Biotene, Peridex, or biosimilars) for subjects experiencing mouth sores.
- 4) Mild strength topical steroid (e.g., hydrocortisone 1% cream) and topical antibiotics (e.g., clindamycin lotion 1.0%) applied at least twice daily starting on Day 1 of study treatment, to baseline affected body areas such as face, chest and upper back with escalation to higher strength and/or oral steroid as detailed in reactive dermatologic toxicity guidelines, Section 10.1.6.3.
- 5) Agents with the potential to dry skin, such as benzoyl peroxide, salicylic acid, acne skin washes, scrubs, exfoliants, anti-aging creams, alcohol (cleansers, wipes) or other agents that can dry skin such as topical retinoids should be avoided unless directed by dermatologist.
- 6) Ketoconazole shampoo may be used for scalp rash.

10.2.6.3 Reactive Treatment of Dermatologic Toxicity (Rash)

This is meant to be in supplement to prophylactic measures undertaken per Section [10.1.6.2](#).

Rash Management (Reactive/Symptomatic) Recommendations Table
--

Subject Group	Prepubescent Subjects		Postpubescent Subjects
Mild Rash	Dermatitis 
 • Add Hydrocortisone 2.5% cream/ointment BID to affected face and skinfolds, consider escalation to Triamcinolone 0.1% ointment on trunk and extremities 	Acneiform Rash 
 • Add Clindamycin lotion 1% BID if not already in use. • Hydrocortisone 2.5% cream/ointment BID can also be added 	Acneiform Rash 
 • Add Clindamycin lotion 1% BID if not already in use. • Hydrocortisone 2.5% cream/ointment BID can also be added, consider escalation to triamcinolone 0.1% ointment
Moderate to Severe Rash	Dermatitis 
 • Add Hydrocortisone 2.5% cream/ointment BID to affected face and skinfolds, consider escalation to Triamcinolone 0.1% ointment on trunk and extremities 	Acneiform Rash 
 • In addition to above systemic antibiotics with: Cephalexin 20mg/kg/day divided BID (with max dose of 500 mg) for up to 6 weeks OR Amoxicillin 25 mg/kg/day divided BID (with max dose of 875 mg) for up to 6 weeks 	
 • Add systemic antibiotic with a tetracycline (e.g. doxycycline or minocycline) for 3 months
Dermatology referral	Dermatitis which is uncontrolled with recommended supportive care or requiring escalation recommend referral to Dermatology. Additional management may include stronger potency topical steroids, additional antibiotics, or oral retinoids.		

Skin toxicity in the form of rash, fissuring, desquamation, or paronychia is a frequent adverse event (AE) in subjects treated with trametinib. We will use the following management, including dose modification.

CTCAE Grade	Adverse Event Management	Action and Dose Modification
Grade 1	Initiate prophylactic and reactive/symptomatic treatment measures Reassess after 2 weeks	Continue treatment If rash does not recover to baseline within 2 weeks despite best supportive care, dose reduction to the next lower dose as per Appendix II .
Grade 2	Initiate prophylactic and reactive/symptomatic treatment measures Reassess after 2 weeks.	Dose reduction: dose reduce to the next lower dose as per Appendix II . Reassess after 2 weeks: 
 • If rash recovers to \leq grade 1 or

		baseline within 2 weeks, increase dose to previous dose level 
 If no recovery to \leq grade 1 or baseline within 2 weeks, interrupt treatment until recovery to grade \leq 1 or baseline, restart with dose reduction to the next lower dose according to Appendix II.
Grade ≥ 3	Escalate reactive/supportive treatment measures to include use of moderate strength topical steroids (Consider a brief period of oral high dose steroid such as methylprednisolone) Consult dermatologist	
 Interrupt treatment until rash recovers to grade ≤ 1 or baseline Restart treatment, dose reduction to the next lower dose according to Appendix II. If no recovery to grade ≤ 2 within 4 weeks, discontinue treatment
Other	If recurrent subjectively intolerable toxicity with at least a week interruption on 2 occasions that is not controlled by optimal supportive medications.	
 Interrupt treatment until rash recovers to grade ≤ 1 or baseline Restart treatment, dose reduction to the next lower dose according to Appendix II. If toxicity remains intolerable discontinue treatment.

10.2.6.4 Treatment Dose Modifications and Guidelines for CK or CPK Elevations

Creatine phosphokinase (CPK) also known as creatine kinase (CK) elevations have been observed in subjects receiving trametinib. To reduce the risk of CPK/CK elevations, subjects will be evaluated with serial lab tests as per [Section 8.1](#). Dose modification and supportive care guidelines for CPK/CK elevations are described in the tables and text below.

Grade	0	1	2	3	4
Creatine phosphokinase (CPK)/Creatine Kinase (CK)	WNL	>ULN to 2.5x ULN	>2.5 to 5x ULN	>5 to 10x ULN	>10x ULN

For Grade 1 or 2 and Grade 3 asymptomatic CPK elevations:

- Maintain dose; continue monitoring as per protocol, or more frequently if clinically indicated.

For Grade 3 symptomatic or Grade 4 CPK elevations:

- This event is considered an DLT.
- Hold treatment until resolution to \leq Grade 1 and dose reduce as per [Section 10.2.3](#)

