10.2.3 Dose Modifications for Non-Hematologic Toxicity

If a subject experiences a dose-modifying non-hematologic toxicity as defined in [Section 10.2.1](#), the treatment will be held.

If the toxicity does not resolve to meet inclusion/exclusion parameters or baseline within 14 days of drug discontinuation the subject must be removed from protocol therapy unless specifically documented in toxicities of special interest [Section 10.2.6](#).

If the toxicity resolves to meet inclusion/exclusion parameters or baseline within 14 days of drug discontinuation the subject may resume treatment with a reduction to the next lower dose according to [Appendix II](#). See [Appendix II](#) for dosing modification in subjects receiving oral solution or the specified dose reduction in subjects receiving tablets.

- Doses reduced for toxicity will not be re-escalated, even if there is minimal or no toxicity with the reduced dose, unless otherwise specified in the toxicities of special interest [Section 10.2.6](#).
- If the same dose-modifying toxicity recurs in a subject who has resumed treatment, the subject must be removed from protocol therapy.

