condition, other concomitant events). Although an adverse drug event may rate only as “possibly related” soon after discovery, it can be flagged as requiring more information and later be upgraded to “probably related” or “definitely related”, as appropriate.

Unlikely: A clinical event, including an abnormal laboratory test result, whose temporal relationship to drug administration makes a causal relationship improbable (e.g., the event did not occur within a reasonable time after administration of the trial medication) and in which other drugs or chemicals or underlying disease provides plausible explanations (e.g., the subject’s clinical condition, other concomitant treatments).

Unrelated: The AE is completely independent of study drug administration, and/or evidence exists that the event is definitely related to another etiology. There must be an alternative, definitive etiology documented by the clinician.

10.10 Treatment Dose Modifications and Guidelines for Adverse Event Reporting specific to study drug

Dose modifying hematological and non-hematological toxicities are defined differently. Dose modification or discontinuation of trametinib for toxicity is considered a dose modifying toxicity. Guidelines for management and dose modifications are also provided for the toxicities of special interest.

Trametinib Dose Modification Schedule for Adverse Events

Grade (CTC-AE)*	Schedule
	Grade (CTC-AE)* Dose Modifications
Grade 1 or Grade 2 (Tolerable)	Continue treatment and monitor as clinically indicated.
Grade 2 (Intolerable) or Grade 3	Interrupt therapy until toxicity is grade 0-1 and reduce by one dose level when resuming therapy.
Grade 4	Discontinue permanently, or interrupt therapy until Grade 0 to 1 and Reduce by one dose level when resuming therapy.

* The intensity of clinical adverse events graded by the Common Terminology Criteria for Adverse Events v4.0 (CTC-AE)

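### Asymptomatic Grade 3 CK attributed to trametinib: Protocol 10.2.6.4 keeps the dose, while 10.2.1.1 with 10.2.3, and the 10.10 table, hold and reduce it

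*Protocol*

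**What the plan says.** Four parts of Section 10 of the Protocol bear on an asymptomatic CK of more than 5 and up to 10 times ULN, which the table in 10.2.6.4 grades as 3.

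- **10.2.6.4 (CK/CPK).** Under "For Grade 1 or 2 and Grade 3 asymptomatic CPK elevations" the dose is maintained and monitoring continues. Only symptomatic Grade 3 or any Grade 4 elevation is called dose-limiting, held, and sent to 10.2.3 for reduction.
- **10.2.1 and 10.2.1.1 (general definition).** For events possibly, probably or definitely attributable to trametinib, the definition covers "Any Grade 3 non-hematological toxicity with the specific exception of" short nausea and vomiting, short fever or infection, and four electrolyte abnormalities that respond to oral supplements. The section opens by pointing to 10.2.6 "for management guidelines for toxicities of special interest".
- **10.2.3 (consequence).** A toxicity that meets the definition leads to a hold. If it resolves within 14 days, "the subject may resume treatment with a reduction to the next lower dose according to" Appendix II. A further bullet reads "Doses reduced for toxicity will not be re-escalated, even if there is minimal or no toxicity with the reduced dose", unless 10.2.6 specifies otherwise.
- **10.10 (general schedule).** The row for intolerable Grade 2 or any Grade 3 says "Interrupt therapy until toxicity is grade 0-1 and reduce by one dose level when resuming therapy". The introduction adds "Guidelines for management and dose modifications are also provided for the toxicities of special interest".

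CK is on the 10.2.6 list of events of special interest ("Creatinine Kinase (CK) or Creatinine Phosphokinase (CPK) elevations").

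**The concern.** The same laboratory value in the same subject gets opposite instructions depending on which section the site opens. One says change nothing. The other two say stop the drug and restart lower.

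Under 10.2.3 the reduction would be lasting, because 10.2.6.4 has no re-escalation clause for CK. It would also use up the single dose reduction that 2.1 allows. Under 10.2.3, failure to resolve within 14 days, or recurrence after restart, means removal from protocol therapy, and 10.2.6.4 exempts CK from neither. At the extreme, the outcomes run from full dose to off treatment.

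The situation is foreseeable. CK is a protocol laboratory test (Table 6-1), and 10.2.6.4 itself says elevations have been seen with trametinib. About 45 subjects over 25 sites (4.7.2) is 45 / 25 = 1.8 per site, so few sites will build up a habit of their own, and consistency depends on the text.

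**Working it through.** The document states no figure to reproduce on this point. The check is a trace of one case through the rules, then the size of the dose step.

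**Trace: asymptomatic CK of 6 times ULN, possibly related to trametinib, first occurrence.**

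| Section | Does the rule apply? | Instruction |
|---|---|---|
| 10.2.6.4 | Yes: Grade 3, no symptoms | Keep the dose, keep monitoring |
| 10.2.1 / 10.2.1.1 | Yes: attributable, Grade 3, non-hematological, CK not excepted | Counts as dose-modifying |
| 10.2.3 | Yes, because 10.2.1.1 is met | Hold; restart at next lower dose |
| 10.10 | Yes: Grade 3 row, no symptom qualifier | Interrupt to Grade 0-1; reduce one level |

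Laboratory values fall within the 10.2.1.1 definition: four electrolyte abnormalities had to be excepted by name.

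**Is there a tie-breaker?**

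- 10.2.1.1 refers the reader to 10.2.6 for management but does not narrow its own definition.
- 10.2.3 defers to 10.2.6 twice: on removal when a toxicity has not resolved at 14 days, and on re-escalation. The hold sentence and the reduction sentence carry no such clause.
- 10.10 says only that special-interest guidelines are provided as well.
- 10.2.6.4 never says that asymptomatic Grade 3 CK is not dose-modifying.

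So no sentence gives 10.2.6 precedence on the hold or the reduction.

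**Size of the reduction, from Appendix II.** Change = (Dose Level -1 minus Dose Level 1) / Dose Level 1.

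| Weight (kg) | Level 1 (mg) | Level -1 (mg) | Change |
|---|---|---|---|
| 11-11.9 | 0.25 | 0.22 | -12% |
| 12-13.9 | 0.30 | 0.24 | -20% |
| 14-15.9 | 0.35 | 0.28 | -20% |
| 16-17.9 | 0.40 | 0.32 | -20% |
| 18-19.9 | 0.45 | 0.36 | -20% |
| 20-22.9 | 0.50 | 0.40 | -20% |
| 23-24.9 | 0.60 | 0.46 | -23% |
| 25-29.9 | 0.70 | 0.50 | -29% |
| 30-34.9 | 0.80 | 0.60 | -25% |
| 35-50 | 1.0 | 0.75 | -25% |
| 50.1-70 | 1.5 | 1.0 | -33% |
| 70.1 and above | 2.0 | 1.5 | -25% |

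The two lowest bands do not fit the pattern and are left out of the range. At 10.0-10.9 kg both levels are 0.2 mg (0%). At 9.0-9.9 kg the listed dose goes from 0.12 to 0.18 mg, but the 0.12 mg entry is labelled as the 0.0125 mg/kg starting dose and so is not a true Level 1 dose.

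**What is not touched.** Section 10.6 records all Grade 3 and higher adverse events whatever the dosing action. The stopping rule in 9.2 counts Grade 4 non-hematologic toxicity plus certain named events, and CK is not among the named ones. Its boundaries therefore do not depend on how this conflict is resolved.

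**The case against.** The strongest reply is that the specific rule governs. Section 10.2.6.4 was written for exactly this case and splits Grade 3 by symptoms. If the general rule won, the Grade 3 part of the keep-dose instruction would have no effect for any attributable event. Section 10.2.1.1 opens by sending the reader to 10.2.6, and adds that modifying or stopping trametinib for toxicity counts as a dose-modifying toxicity; 10.10 repeats this. On that reading, what 10.2.6 does with the dose decides the status, and asymptomatic Grade 3 CK changes nothing. Other sections also depart from the 10.10 Grade 3 row: Grade 3 diarrhea that resolves within 72 hours, visual events with retinal detachment and vein occlusion excluded, and liver enzyme elevations that resolve within 7 days may all resume without reduction. That makes 10.10 look like a default schedule.

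Most of this stands as evidence of intent, and most sites would probably keep the dose. It does not settle the text. The added note widens the definition of dose-modifying toxicity; it does not say that only events leading to a dose change qualify. The authors wrote explicit deference to 10.2.6 where they wanted it in 10.2.3, and wrote none for the hold or the reduction. The liver section also states when a Grade 3 value becomes dose-modifying, which the CK section does not.

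It is also fair that the 12% to 33% range is the size of the step for any toxicity. It does not measure how often a site would take the wrong path. And the missing precedence sentence is a wider drafting gap, of which CK is one clear case.

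**Conclusion.** The conflict is real and the text is wrong as written: operative rules give opposite dosing for one attributable asymptomatic Grade 3 CK value, and nothing in the Protocol ranks them. It is minor and should be corrected. Each affected event gives either no dose change or a hold followed by a reduction of 12% to 33% at 11 kg and above, with no re-escalation and with removal possible under 10.2.3.

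The conclusion rests on two conditions: the event is judged at least possibly related to trametinib (10.2.1 applies only then), and the site reads the general sections literally. How often asymptomatic Grade 3 CK will occur is not stated, so no expected number of affected subjects can be given. The consequence is uneven dosing across sites. Event recording and the 9.2 toxicity boundaries are unaffected.

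**What to change.** 1. In 10.2.1.1, add asymptomatic Grade 3 CK/CPK elevation to the list of Grade 3 exceptions.
2. In 10.2.1.1, 10.2.3 and 10.10, add one sentence: for events of special interest, the rules in 10.2.6 govern hold, reduction and restart, and the general rules apply only where 10.2.6 is silent.

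The second change also settles the diarrhea and visual-event departures from the 10.10 table. The cost is amendment wording only: one bullet, and one sentence in three places. Sample size, endpoints, visit schedule and stopping boundaries stay as they are.
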